[contact]

[contact]

LIST OF ABBREVIATIONS

ACD Anterior Chamber Depth

AE Adverse Event

BCDVA Best Corrected Distance Visual Acuity

CRO Clinical Research Organization

CRF Case Report Form

D Diopter

DCNVA Distance Corrected Near Visual Acuity

eCRF electronic Case Report Form EDC Electronic Data Capture

ETDRS Early Treatment Diabetic Retinopathy Study

FDA Food and Drug Administration

ICF Informed Consent Form

IDE Investigational Device Exemption

IOL Intraocular Lens
IOP Intraocular Pressure
IRB Institutional Review Board

m Meter mm Millimeters

mm Hg Millimeters of Mercury

NAVQ Near Acuity Visual Questionnaire

OD Right eye OS Left eye

PI Principal Investigator
PMMA Polymethylmethacrylate
PRO Patient Reported Outcomes
SAE Serious Adverse Event

OAL Sellous Adverse Everit

SPK Superficial Punctate Keratitis

UADE Unanticipated Adverse Device Effect
UCDVA Uncorrected Distance Visual Acuity
UCIVA Uncorrected Intermediate Visual Acuity

UCNVA Uncorrected Near Visual Acuity

USA United States of America VMI VisAbility™ Micro Insert

VMIS VisAbility™ Micro Insert System

VIS-2014-5YR

THREE YEAR ADDITIONAL FOLLOW-UP OF SUBJECTS PREVIOUSLY COMPLETING TWO YEAR PARTICIPATION IN PROTOCOL VIS-2014

1.0 STUDY OUTLINE

1.1 STUDY OBJECTIVE

The objective of this study is to obtain an additional 36 months of safety and effectiveness data from all subjects who were implanted or explanted in Protocol VIS-2014, a prospective, multicenter clinical trial of the VisAbility™ Micro Insert System in presbyopic emmetropes.

1.2 INDICATIONS FOR USE

The VisAbility Micro Insert is indicated for bilateral scleral implantation to improve unaided near vision in phakic, presbyopic patients between the ages of 45 and 60 years of age, who have a manifest spherical equivalent between -0.75 D and +0.50 D with less than or equal to 1.00 D of refractive cylinder in both eyes and require a minimum near correction of at least +1.25 D reading add.

1.3 SUBJECT POPULATION

Subjects who were implanted or explanted with the VisAbility™ Micro Insert in Protocol VIS-2014 will be invited to participate.

Each subject will be contacted and asked to participate in this follow-up study. Three documented attempts will be made by either regular mail, phone call, text, or email to contact each subject.

Once contacted, study staff will explain the study purpose, procedures, and responsibilities to each potential participant. Subjects who agree to participate must sign the informed consent, be able to understand the study requirements, be willing to follow study instructions, and agree to return for required follow-up visits.

If all three attempts to contact the subject are unsuccessful, a certified letter will be sent to the last known address of the subject and a copy of the certified letter will be retained at the study site. If there is no response from the subject over the course of the study, he/she will be deemed not enrolled at the close of the 60-month window.

1.4 STUDY DESIGN

VIS-2014-5YR is a multicenter, observational study to evaluate the long-term safety of the VisAbility Micro Inserts in subjects who were implanted or explanted with the VisAbility™ Micro Insert in the VIS-2014 clinical trial. Study subjects will be examined at 36-, 48-, and 60-months post-operatively (based on the anniversary of their first VisAbility™ surgery) with no planned interventions. Subjects who opt to have all implant segments bilaterally removed (explanted) after enrollment in VIS-2014-5YR will be followed for 2 years post removal, up to a maximum of 5 years follow-up. Additional visits may include but are not limited to examination at day 1, week 1, month 1, and 2 annual visits, post removal.

1.5 SAMPLE SIZE

All subjects who were implanted or explanted with the VisAbility Micro Insert will be invited to participate. Actual sample size will be determined at the completion of enrollment.

1.6 DATA ANALYSES

Descriptive statistics and summaries will be provided for primary eyes and all eyes for the following:

Primary safety outcomes:

- Partial explantation (1–3 Micro inserts per eye) or complete explantation (4 Micro inserts per eye) and reason(s)
- Anterior Segment Ischemia (Grades 2 4)
- Segment exposure due to conjunctival and/or scleral erosion
- Rate of serious adverse events (SAEs)

Secondary safety outcomes:

- Best Corrected Distance Visual Acuity (BCDVA)
- IOP increase > 10 mm Hg over baseline or IOP > 30 mm Hg
- Slit Lamp findings
- Fundus exam findings
- Rate of adverse events (AE's)

Secondary effectiveness outcome:

 Change in uncorrected and distance corrected near visual acuity and letters correct in the primary eye of bilaterally implanted subjects (with all eight implants in place), as compared to baseline (VIS-2014).

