4.2 EXAMINATION SCHEDULE

Visit windows are calculated based on a 30-day month. The visit windows are based on the anniversary of the first VisAbility surgery. The examination schedule is as follows:

- Month 36 (+/- 60 days postoperative)
- Month 48 (+/- 60 days postoperative)
- Month 60 (+/- 60 days postoperative)

Subjects may be consented and enrolled at any time between the opening of the 36-month window and the close of the 60-month window. Visit data for subjects examined between visit windows for the 36, 48, and 60 month exam will be considered out-of-window.

Subjects who opt to have all implant segments bilaterally removed (explanted) after enrollment will be followed for 2 years post removal, up to a maximum of 5 years follow-up. Additional visits may include but are not limited to examination at day 1, week 1, month 1, and 2 annual visits, post removal.

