5.3 ANALYSIS OF CLINICAL PARAMETERS

Means, standard deviations, and ranges (min/max) will be derived from the continuous measurements. Frequencies, rates (cumulative incidence), and proportions will be used for summarizing the categorical and ordinal outcomes.

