6.0 ADVERSE EVENT REPORTING

An Adverse Event (AE) is any untoward sign, symptom or disease observed during the study regardless of the suspected cause. Conditions or diseases that are pre-existing or chronic but stable are not Adverse Events. Changes in pre-existing or chronic conditions or diseases that are consistent with natural disease progression are not Adverse Events.

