6.3 ADVERSE EVENT ASSESSMENT

All study subjects will be evaluated for Adverse Events as defined in this protocol. All adverse events, regardless of severity, and whether or not they are ascribed to the study treatment, will be recorded in the source documents using standard medical terminology. Pre-existing conditions or diseases present at the 36-month exam that remain stable or change in a manner consistent with natural disease progression are not considered Adverse Events.

All Adverse Events will be evaluated beginning at the time of onset, and evaluation will continue until resolution or until the investigator determines that the subject's condition is stable. The investigator will take appropriate and necessary therapeutic measures required for resolution of the Adverse Event. Any medication necessary for the treatment of an Adverse Event must be recorded on the concomitant medication source document.

All AEs will be characterized by the following criteria:

- Event term,
- Intensity or severity,
- Expectedness,
- · Relationship to study treatment,
- Outcome, and
- Treatment or action taken.

Whenever possible, recognized medical terms should be used when recording AEs. Colloquialisms and/or abbreviations should not be used. Only one medical concept, preferably a diagnosis instead of individual symptoms, should be recorded as the event.

If known at the time of reporting, a diagnosis (i.e., disease or syndrome) should be recorded on the source document rather than individual signs and symptoms (e.g., record congestive heart failure rather than dyspnea, rales, and cyanosis). If a constellation of signs and/or symptoms cannot be characterized with a single medical diagnosis or syndrome, and they are considered unrelated to an encountered syndrome or disease at the time of reporting, these individual events should be recorded as separate AEs (e.g., if congestive heart failure and severe headache are observed at the same time, each event should each be recorded as an individual AE). If a diagnosis was not initially reported and is subsequently established, it should be reported as follow-up information and the original AE documents updated accordingly.

Adverse Events occurring secondary to other events (e.g., sequelae) should be identified by the primary cause. A "primary" event, if clearly identifiable, should represent the most accurate clinical term to record as the AE event term. For example:

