6.8 POSSIBLE ADVERSE EVENTS

Possible Adverse Events that might reasonably be expected to occur in this study are listed below. The time periods refer to the exam visit that occurs corresponding to the post-operative follow-up visit schedule (i.e., 36 months means the 36-month postoperative visit).

These specific examples of possible Adverse Events for VIS-2014-5YR include, but are not limited to:

Lids and Lashes

- Ptosis
- Hordeolum
- Chalazion
- Onset of or worsening to severe clinically significant lid margin disease (e.g., blepharoconjunctivitis, blepharitis, meibomitis, meibomian gland dysfunction, etc.)

Cornea

- Corneal dellen
- Corneal abrasion > 2mm
- Dry eye signs (moderate or severe) of corneal and/or conjunctival staining, etc., requiring prescription medication
- Corneal edema (moderate or severe)
- Corneal infiltrate or ulcer

Conjunctiva/Sclera

- Conjunctival cyst
- Conjunctival erosion
- Moderate or severe conjunctival injection
- Subconjunctival hemorrhage (not associated with an explant or concomitant procedure)
- Conjunctivitis (allergic, bacterial, viral)
- Scleral erosion
- Scleritis

Anterior Segment, Iris, Lens

- Persistent pupil abnormalities
- Posterior Synechiae
- Rubeosis Irides
- Anterior segment ischemia (Grades 2 4)
 - Grade 2: Decreased pupil reactivity (%CH < 25%)
 - Grade 3: Decreased pupil reactivity plus anterior chamber reaction (Grade 2 with cell and/or flare)
 - Grade 4: Corneal edema, anterior chamber reaction and decreased pupillary reactivity (Grade 3 with striate keratopathy)
- Anterior chamber cells or flare
- Intraocular Inflammation other than anterior chamber cells and flare (e.g. Vitritis)
- Two grade change in lens opacity as compared to preoperative baseline

Implants

Displaced, extruded, or missing implant segments

Intraocular Pressure

- Glaucoma
- Hypotony (IOP < 6 mm Hg)
- Increase in IOP of > 10 mm Hg over baseline or IOP > 30 mm Hg at two consecutive visits

BCDVA Loss

Decrease in BCDVA of greater than or equal to 2 lines (≥ 10 letters ETDRS)

Fundus

- Choroidal effusion
- Retinal detachment
- Retinal or vitreous hemorrhage
- Retinal hole
- Posterior vitreous detachment

Secondary Surgical Intervention

- Implant segment removal
- Exposed implant segments or conjunctival retraction requiring conjunctival reapproximation
- Cataract extraction
- Any other secondary surgical intervention

Other

- Eye pain requiring oral prescription pain medication

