Cell and flare will be graded according to the SUN grading scheme (using a 1x1 mm slit lamp beam):

SUN Grading for AC Cells

GRADE	CELLS IN 1x1mm Field				
0	0	(None)			
0.5+	1-5	(Faint)			
1+	6-15	(Mild)			
2+	16-25	(Moderate)			
3+	26-50	(Marked)			
4+	50+	(Severe)			

SUN Grading for AC Flare

GRADE	Description
0	None
1+	Faint
2+	Moderate (iris/lens details clear)
3+	Marked (iris/lens details hazy)
4+	Intense (fibrin/plastic aqueous)

Iris appearance

- 1 = Normal
- o 2 = Diffuse atrophy
- 3 = Segmental atrophy
- 4 = Sectoral contraction
- Other abnormal iris findings

Assessment of Anterior Segment Ischemia

- Grade 2: Decreased pupil reactivity (%CH < 25%)
- Grade 3: Decreased pupil reactivity plus anterior chamber reaction (Grade 2 with cell and/or flare)
- Grade 4: Corneal edema, anterior chamber reaction and decreased pupillary reactivity (Grade 3 with striate keratopathy)

Intraocular Pressure

Intraocular pressure will be measured using Goldmann applanation tonometry. Measurements will be taken according to the published guidelines set forth by Michael A. Kass [Kass MA. Standardizing the measurement of intraocular pressure for clinical research. Guidelines from the Eye Care Technology Forum. Ophthalmology. 1996 Jan;103 (1):183-5]. Copies of this guideline will be provided to all sites.

Posterior Segment Examination

Posterior segment examination should include a full dilated fundus examination and will be assessed using a 20D condensing lens. Abnormalities of any of the structures in any location of the fundus should be noted. Examination may include but is not limited to: vitreous body, optic disc, vasculature, macula, and periphery.

Peripheral Fundus Examination

- Normal
- Abnormal (if abnormal, please describe)

Cup to Disc Ratio will be assessed by means of a fundus exam using condensing lenses (78 D/90 D) and the slit lamp biomicroscope.

Other Observations:

Photographs, drawings and/or standard descriptive ophthalmic terms may be used as needed to describe any other ocular findings.

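### The raised-IOP safety outcome has no rule for eyes on pressure-lowering treatment, so some treated rises can be counted as event-free

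*Combined protocol and SAP*

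**What the plan says.** Section 1.6 lists, among the secondary safety outcomes, "IOP increase > 10 mm Hg over baseline or IOP > 30 mm Hg". The entry has two numeric thresholds and no term for treatment. Appendix 1 gives the measurement: "Intraocular pressure will be measured using Goldmann applanation tonometry". It describes no adjustment for eyes under treatment.

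Section 5.3 gives the summaries: "Frequencies, rates (cumulative incidence), and proportions will be used for summarizing the categorical and ordinal outcomes". It does not say which of these applies to IOP. Section 5.2 makes the analysis descriptive and includes all enrolled subjects.

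Section 4.2 sets the exams: "Month 36 (+/- 60 days postoperative", with the same tolerance at months 48 and 60, counted in 30-day months. Sections 4.1.2 and 4.2 allow enrollment until the 60-month window closes.

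On recording, section 6.3 states "All adverse events, regardless of severity, and whether or not they are ascribed to the study treatment, will be recorded" and "Any medication necessary for the treatment of an Adverse Event must be recorded on the concomitant medication source document". Section 6.0 adds that "Changes in pre-existing or chronic conditions or diseases that are consistent with natural disease progression are not Adverse Events", and 6.3 applies a similar exclusion to conditions present at the 36-month exam. Section 6.8 lists, as a possible adverse event, "Increase in IOP of > 10 mm Hg over baseline or IOP > 30 mm Hg at two consecutive visits". Neither the parameter list in 4.3 nor Table 1 includes a medication review.

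**The concern.** The study is observational, and no section restricts ocular treatment. A subject whose pressure rises may be treated in usual care. If treatment works, the next study reading is in range and the threshold outcome records nothing. The imputation text in 5.2 does not help, because the eye has an observed value and nothing is missing.

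Treated eyes are plausibly those with the worse pressure course. Losing them would make the long-term pressure profile of the device look better than it is. There is no comparator arm in which the same loss would occur, so the reported rate stands alone as evidence. The problem arises with any choice of baseline and with a single qualifying reading.

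**Working it through.** The plan states no expected IOP event rate and no treatment rate, so it has no figure of its own to reproduce. The check has three parts.

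**1. Time without a scheduled reading** (inputs from 4.2: 30-day months, ±60 days)

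Window = 30 × month ± 60 days.

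- Month 36: 1080 ± 60 = days 1020 to 1140
- Month 48: 1440 ± 60 = days 1380 to 1500
- Month 60: 1800 ± 60 = days 1740 to 1860

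Gap between windows: 1380 − 1140 = 240 days, and 1740 − 1500 = 240 days.

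Before enrollment: nominal month 24 is day 24 × 30 = 720. The first reading in this study may fall between 1020 − 720 = 300 and 1860 − 720 = 1140 days later.

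**2. Which treated eyes are missed**

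- *Rise and treatment wholly between study exams:* missed under any summary in 5.3.
- *Rise and treatment before enrollment:* missed under any summary if the pressure is controlled at entry and stays so.
- *High reading at a study exam, then treatment:* kept under cumulative incidence. In a visit-by-visit proportion it appears as an event at that visit and as event-free at later ones. Section 5.3 permits both summaries.

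The adverse event route is partial for four reasons:

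- A pressure condition that arose and was controlled before the 36-month exam, and is then stable or progresses naturally, falls under the exclusion in 6.3.
- The medication instruction in 6.3 covers drugs given for an adverse event, so the protocol does not require treatment of an excluded condition to be recorded.
- The IOP entry in 6.8 needs two consecutive visits, about 12 months apart on the schedule. Treatment after the first high reading can prevent the second.
- Where treatment is recorded, no section connects it to the IOP outcome.

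**3. Illustration of size** (all inputs assumed; none is in the documents)

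Reported proportion = p × (1 − g). Here p is the true proportion of eyes ever above threshold, and g is the share of those eyes treated back below threshold before any study reading.

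| p | g = 0 | g = 25% | g = 50% | g = 75% | g = 100% |
|---|---|---|---|---|---|
| 2% | 2.0% | 1.5% | 1.0% | 0.5% | 0% |
| 5% | 5.0% | 3.75% | 2.5% | 1.25% | 0% |
| 10% | 10.0% | 7.5% | 5.0% | 2.5% | 0% |

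For example, 0.05 × (1 − 0.50) = 0.025. At g = 0, where every rise is read at a study exam before treatment and summarized cumulatively, there is no undercount.

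**The case against.** The strongest reply is that the plan already has two safeguards.

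First, 5.3 names cumulative incidence. Under that summary an eye read high at a study exam stays an event whatever follows. This stands, but 5.3 does not assign that summary to IOP, and it cannot help an eye never read high in the study.

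Second, the adverse event net is wide. Section 6.0 covers any untoward finding whatever the cause, and the list in 6.8 is not exhaustive. It names glaucoma and any other secondary surgical intervention. Sections 6.3 and 6.7 require the treatment or action taken to be documented, and the adverse event rate is itself an outcome in 1.6. A new treated rise after enrollment, and pressure-lowering surgery in particular, can therefore reach the reported safety results. This also stands. It does not reach the IOP line, and it leaves out the excluded conditions described above. The medication form and the eCRF are not in the documents and may capture more than the protocol requires.

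A reader might infer that every treated eye is lost, that pressure is deliberately read regardless of treatment, or that the masking could never be detected. The documents support none of these. They are silent on treatment, they allow a summary that keeps some treated eyes, and they require drugs given for an adverse event to be recorded. Nor do they show that the undercount grows from month 36 to month 60.

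Finally, this is one secondary outcome in a descriptive study with no hypothesis test on it. That limits the stakes.

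**Conclusion.** The point holds in a limited form. The IOP outcome rests on observed pressure with no rule for treated eyes. A rise treated between windows or before enrollment can be counted as event-free, as can an eye treated after a high reading when results are tabulated by visit. Adverse event reporting closes only part of the gap.

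Relative to the number of eyes that ever crossed a threshold, masking by treatment can only lower the count. The direction is therefore known, but the size is not: the documents give neither an event rate nor a treatment rate, and the loss may be small or nil. The conclusion assumes that some subjects receive effective pressure-lowering treatment outside study exams, which the plan neither prevents nor tracks. It is best treated as a cheap improvement.

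**What to change.** - **Sections 4.3 and 6.3:** at each visit, record IOP-lowering medication, laser or surgery, with start date and reason, whether or not it is linked to an adverse event.
- **Sections 1.6 and 5.3:** keep the threshold outcome, and name per-eye cumulative incidence over all exams, including out-of-window ones, as its summary.
- **Beside it, report** the number of eyes with IOP-lowering treatment started or intensified, split into before and after enrollment, and the number meeting either component.
- **IOP means:** flag treated eyes.

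Replacing the threshold outcome with a composite dated from the VIS-2014 preoperative baseline is not needed. It would bring in treatment begun during the earlier trial and treatment never preceded by a threshold pressure.

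The cost is one question per visit and one derived variable. Some treatment starts will be unrelated to the device, and separate reporting makes that visible. The change concerns recording and analysis only; no clinical rule is proposed.

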1.7 CLINICAL PARAMETERS

The following clinical parameters will be measured:

- Near visual acuity (uncorrected, distance corrected)
- Distance visual acuity (uncorrected and best corrected)
- Intermediate visual acuity (uncorrected)
- Patient Preferred Distance
- Minimum add to 20/20
- Dynamic pupillometry
- Corneal Topography/Keratometry
- Manifest refraction
- IOP
- Slit lamp biomicroscopy
- Indirect Ophthalmoscopy
- Cup/Disc Ratio

A full description of the examination schedule and clinical parameters for the entire 5-year study can be found in Table 1.

TABLE 1: SCHEDULE OF VISITS AND MEASUREMENTS

		Initial							2014 w-up	VIS-2014-5YR Follow-up				
	Pre- Op	0 Day	1 Day	1 Wk	1 Mo	2 Mo	3 Mo	6 Mo	12 Mo	18 Mo	24 Mo	36 Mo	48 Mo	60 Mo
Slit Lamp Biomicroscopy OD, OS	√ ²		√	√	√	√	√	✓	✓	√	√	✓	✓	√
Applanation Tonometry OD, OS	$\sqrt{2}$		✓	√	✓	✓	✓	✓	✓	√	✓	✓	✓	√
Gonioscopy OD, OS	✓								✓					
Scleral Thickness Measurement OD, OS	√													
Implant Assessment OD, OS					√			√	✓		✓	√	√	✓
Axial Length / ACD OD, OS	✓								✓		✓			
Corneal Topography/ Keratometry OD, OS	✓											✓	✓	✓
Dynamic Pupillometry OD, OS	$\sqrt{2}$	✓	✓	√	√	✓	✓	✓	✓	✓	✓	√	✓	✓
Posterior Pole exam with 78 /90D lens OD, OS	$\sqrt{2}$		√		✓	✓	✓	✓		✓		✓	✓	√
Dilated Indirect Ophthalmoscopy 20/30D lens OD, OS	√			✓					√		√	√	√	✓
Visual Fields OD, OS	✓													
Cup/Disk Ratio OD, OS	✓								✓		✓	✓	✓	✓
Cycloplegic Refraction w/ VA - OD, OS	√								√		✓			
Manifest Refraction OD, OS	√			√	✓	✓	✓	✓	✓	✓	✓	✓	√	√
BCDVA OD, OS, OU	√2			✓	✓	✓	✓	✓	✓	✓	√	✓	✓	✓
UCDVA OD, OS, OU	✓		√1	✓	✓	✓	✓	✓	✓	✓	✓	✓	✓	✓
UCNVA @ 40 cm OD, OS, OU	✓				_		✓	√	✓	√	✓	√	√	✓
UCIVA @ 66 cm OU	✓						✓	✓	✓	✓	✓	✓	✓	√
DCNVA @ 40 cm OD, OS, OU	✓				√	√	√	√	√	√	√	√	√	√
Patient Preferred Distance DCN - OD, OS, OU	√						√	√	√	√	√	√	√	✓
Minimum add to 20/20	√						√3	√3	√3	√3	√3	√	✓	✓
NAVQ (Validated PRO) & Subject Questionnaire	✓							✓	✓	✓	√			
Sub-Study Only Wavefront measurements ³	>						✓	√	>	√	√			
Sub-Study Only Defocus Curve ³ ¹ Visual acuity will be measured	√						√	√	✓	✓	✓			

¹Visual acuity will be measured using pinhole on day 1 ²Fellow Eye Safety Exam (when fellow eye surgery is 61-180 days after primary eye surgery)

³Randomized Sub-study subjects only – control group subjects are examined through 6 months and the surgery group through 24 months.

